We will add apremilast to their treatment regimen according to the approved dosage for psoriasis and psoriatic arthritis: 10 mg orally one time on day 1, 10 mg orally twice daily on day 2, 10 mg orally in

AM and 20 mg orally in PM on day 3, 20 mg orally twice daily on day 4, 20 mg orally in AM and 30 mg orally in PM on day 5, then 30 mg orally twice daily thereafter.

7. Brief Study Synopsis: With limited treatment options available for dermatomyositis, we hypothesize that apremilast, a phosphodiesterase-4 (PDE-4) inhibitor, is a safe and efficacious add-on treatment in patients with recalcitrant cutaneous dermatomyositis.

The study will investigate the efficacy, safety and toxicity of apremilast given at 30 mg twice daily to patients with recalcitrant cutaneous dermatomyositis. Clinical response will be assessed at 1 and 3 months. Patients will also be evaluated for durability of their response for up to 6 months.

Treatment will be monitored with frequent clinical visits (0, 1, 3 and 6 months) and blood tests (CBC, CMP, CK, aldolase). Treatment will be discontinued at disease progression or unacceptable adverse events. Disease progression is defined as a 4 points increase in CDASI score, worsening of muscle disease by MMT-8 score and 5 points increase in DLQI.

5 mm skin biopsies from lesional skin will be performed before treatment with apremilast and after 3 months of treatment for gene expression profiling and confirmatory immunohistochemical stains.

8. Inclusion Criteria:

- Must understand the risks and the benefits/purpose of the study and provide signed and dated informed consent.
- Must be 18 years at time of signing the informed consent form.
- Willing to participate in all required evaluations and procedures in the study including the ability to swallow pills without difficulty.
- Patients must have a diagnosis of DM based upon the characteristic cutaneous findings proposed by Sontheimer^[6] and/or a skin biopsy consistent with DM.
- Patients must be candidate for systemic therapy for their DM skin disease defined by inadequate response to aggressive sun protection along with the use of potent topical corticosteroids and/or immunomodulators.
- Patients with a diagnosis of dermatomyositis on steroid-sparing agent and/or systemic steroids (maximum dose of prednisone 1mg/Kg) and still having cutaneous disease activity of at least 5 on the CDASI scale.

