- If on immunosuppressive treatments and/or steroids, patients must be on stable doses for at least 4 weeks (28 days).
- Patients must undergo age appropriate cancer screening.
- Females of childbearing potential (FCBP) must have a negative pregnancy test at screening (day 0 of the study and every month throughout the study). While on investigational product and for at least 28 days after taking the last dose of investigational product.

- **9. Exclusion Criteria:**

- Increasing or changing dose of topical therapy within 14 days of study day 0 (including but not limited to topical corticosteroids, tacrolimus, pimecrolimus).
- Increasing or changing systemic steroids dosing within 28 days of study day 0.
- Increasing or changing dosing for concurrent therapy agents within 28 days or 5 half-lives of the biologic agent, whichever is longer, before study day 0: methotrexate, azathioprine, mycophenolate mofetil, hydroxychloroquine, dapsone, leflunomide, cyclosporine, biologic agents (anti-TNFs), IVIG, rituximab.

- History of any clinically significant (as determined by the investigators) cardiac, endocrinologic, pulmonary, neurologic, psychiatric, hepatic, renal, hematologic, immunologic, or other major uncontrolled disease.
- Any condition, including the presence of laboratory abnormalities, which places the patient at unacceptable risk if he/she were to participate in the study or confounds the ability to interpret data from the study.
- Pregnant or breastfeeding.
- Untreated Latent Mycobacterium tuberculosis infection or active tuberculosis infection as indicated by a positive Purified Protein Derivative (PPD) skin test or T-spot.
- Any condition, including the presence of laboratory abnormalities that places the patient at unacceptable risk if he/she were to participate in the study or confounds the ability to interpret data from the study.
- Patients with acute dermatomyositis onset and rapid progression of muscle disease or significant systemic involvement including pulmonary diseases associated with DM.
- Prior major surgery or major life-threatening medical illness within 2 weeks.
- Inflammatory bowel disease, malabsorption or any other gastrointestinal motility disorders that limit the absorption of the study drug.
- Active hepatitis B or C infection with detectable viral nucleic acid in the blood or known Human Immunodeficiency Virus (HIV) positivity.

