RNA extracted from skin biopsies collected before and after *in vivo* treatment with apremilast (as detailed above) will be subjected to RNA sequencing. Illumina strand-specific TruSeq libraries will be prepared from the polyA selected RNA and subjected to 1x100 base sequencing on an Illumina HiSeq2500 machine. The number of samples proposed here (10 samples before treatment and 10 samples after treatment) is expected to yield sufficient statistical power for this approach; smaller numbers have been used in similar approaches to investigate drugs' mechanism of action (usually three samples).^[7-9]

RNA-seq analysis will be performed in conjunction with the Tulane Cancer Crusaders Next Generation Sequence Analysis Core (Tulane Cancer Center - <https://tulane.edu/som/cancer/research/core-facilities/cancer-crusaders/>). Gene and isoform expression will be determined using RSEM^[10] and differential expression will be analyzed using EB-seq.^[11] Genes that are identified as differentially expressed between the two groups with a False Discovery Rate (FDR) of < 0.05 will be subjected to analysis by *Ingenuity* (IPA, Redwood City, CA). This analysis will group the identified genes into specific pathways, cell types, or disease process. A similar approach will be conducted using *Gene Set Enrichment Analysis (GSEA)*. These experiments and GEP analysis will be performed in conjunction with our collaborator's ([name]) lab, given his extensive experience in this field.^[12, 13]

b. Protein analysis

Information identified by Ingenuity or GSEA (signaling pathways, regulatory molecules, etc...) will be verified using IHC staining on select samples.

IV. OBJECTIVES AND ENDPOINTS

1.Primary Objective Description

To determine the overall response rate (ORR) of apremilast in cutaneous disease of patients with recalcitrant dermatomyositis at 3 months.

The ORR will be measured using the Cutaneous Dermatomyositis Activity and Severity Index (CDASI) at months 0, 1, and 3.

CDASI is a validated tool to measure skin disease activity in dermatomyositis.^[14] ORR includes partial and complete responses. Complete response is defined by a CDASI score of zero. Partial response is defined by a decrease of CDASI score of at least 4 points. Calculation is performed as the CDASI score at 1, and 3 month(s) minus the score at baseline.

All investigators (PI and Sub-Is) will be trained on how to screen the patients per the CDASI score tool.

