Photograph of skin rash will be taken at months 0,1 and 3 and compared to baseline.

2. Secondary Objective(s) Description

To determine the durability of responses for up to 6 months on apremilast for responders at 3 months. The durability of responses includes partial and complete response durability. The durability of response will be measured using the CDASI at 6 months minus CDASI at 3 months. Complete response durability is defined as zero or minus difference between CDASI score at 6 months and CDASI score at 3 months. Partial response is defined as >4 points difference between CDASI score at 6 months and CDASI score at 3 months.

We will assess the response of all patients at 6 months to identify possible delayed response. Complete response is defined by a CDASI score of zero at 6 months. Partial response is defined by a decrease of CDASI score of at least 4 points at 6 months compared to baseline. Calculation is performed as the CDASI score at 6 month(s) minus the score at baseline.

Photograph of patient's rash will be taken at 6 months and compared to 3 months and baseline.

To determine the safety and toxicity of apremilast when administered at 30 mg twice daily in patients with dermatomyositis. The safety assessment will include the assessment of adverse events, serious adverse events, laboratory testing and physical examination.

An additional secondary endpoint will be to determine if patients who experience remission of their disease can be maintained on apremilast as monotherapy.

To determine the patient quality of life using the Dermatology Life Quality Index (DLQI)^[15] at baseline, 1, 3 and 6 months.

Patient will be assessed 1 month after discontinuing apremilast (follow up visit) to assess change in response post discontinuation of apremilast. Patients will be examined and, CDASI, MMT-8 and DLQI will be performed. Photograph of patient's rash will be taken. CBC, CMP, CK, aldolase and urine pregnancy test will be performed.

3. Exploratory Objectives:

We will measure muscle enzymes (creatin kinase (CK) and aldolase) at 0, 1, 3, and 6 month(s) of apremilast in patients with muscle disease.

We will assess disease activity using the manual muscle testing-8 (MMT-8) in patients with muscle disease.^[16]

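### Background therapy must be stable only at entry, and nothing states how later changes are recorded or analysed, so a CDASI fall after a background increase counts as an apremilast response

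*Combined protocol and SAP*

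**What the plan says.** **Design.** Treatment and Dosing (item 6): "We will add apremilast to their treatment regimen according to the approved dosage for psoriasis and psoriatic arthritis". The planned enrolment is 10 (Section V), and no comparator is described.

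**Background therapy.** Every statement on stability is an eligibility criterion.
- Inclusion Criteria (item 8): "If on immunosuppressive treatments and/or steroids, patients must be on stable doses for at least 4 weeks (28 days".
- Exclusion Criteria (item 9), topical agents: "Increasing or changing dose of topical therapy within 14 days of study day 0".
- Exclusion Criteria, steroids: "Increasing or changing systemic steroids dosing within 28 days of study day 0".
- Exclusion Criteria, other immunosuppressants and biologics: changed dosing of "concurrent therapy agents within 28 days or 5 half-lives of the biologic agent, whichever is longer, before study day 0".

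**Endpoints.** Section IV.1 takes the visit CDASI minus the baseline CDASI. Complete response is a score of zero, and "Partial response is defined by a decrease of CDASI score of at least 4 points". Section IV.2 repeats this for delayed response: "Partial response is defined by a decrease of CDASI score of at least 4 points at 6 months compared to baseline". Durability in the month-3 responders is the month-6 score minus the month-3 score. None of these definitions mentions background therapy. Section IV.2 also asks whether patients in remission can be kept on apremilast alone.

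**Analysis and records.** Section VI lists descriptive proportions and mean changes, with LOCF for missing data. It has no rule for changed background therapy and lists no analysis for the monotherapy question. The Schedule of Events has no medication row, and Medical History is marked only at screening and day 0. Section X describes the CRF in general terms.

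**The concern.** The primary objective presents the response rate as that of apremilast. In an uncontrolled add-on study, nothing in the data separates the added drug from a simultaneous change in the regimen it was added to. The entry criteria remove recent changes before day 0, but the primary endpoint is three months later and the last efficacy assessment on treatment is at six.

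An increase in background therapy would push the month-1, month-3 and month-6 response rates upward. An increase between months 3 and 6 could hold a score down and make a response look durable. A reduction could push the same figures the other way. The monotherapy endpoint makes reductions a foreseeable part of the study, and it cannot be evaluated without knowing when background drugs were reduced or stopped.

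What is at stake is whether a reader of a 10-patient result can tell how much of it depends on such changes.

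**Working it through.** **1. Do the entry windows reach the endpoint?** The criterion for immunosuppressants and biologics says explicitly that its window lies before day 0. The topical and steroid criteria refer to 14 and 28 days around day 0 without saying before. Even if these two were read as also running forward, they would end at day 14 and day 28, short of month 3.

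**2. How is a patient with a background increase classified?** Take a patient whose steroid dose rises in month 2 and whose CDASI at month 3 is 4 points below baseline. The score is present, so LOCF does not apply. The partial-response definition is met and no other condition exists. The patient is a responder.

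**3. Weight on the response rate.** The plan gives no null rate, target rate or power for the ORR, so there is no figure of its own to reproduce. With n = 10, one converted patient changes the rate by (x + 1)/10 − x/10 = 1/10, or 10 percentage points. No converted patient means no change. Exact (Clopper-Pearson) 95% limits are the 2.5% quantile of Beta(x, n − x + 1) and the 97.5% quantile of Beta(x + 1, n − x):

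| Responders (assumed) | Rate | Exact 95% CI |
|---|---|---|
| 2/10 | 20% | 2.5% to 55.6% |
| 3/10 | 30% | 6.7% to 65.2% |
| 4/10 | 40% | 12.2% to 73.8% |
| 5/10 | 50% | 18.7% to 81.3% |

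The neighbouring intervals overlap widely.

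**4. Weight on durability.** The denominator is the number r of month-3 responders, so one patient weighs 100/r points: 33.3 for r = 3, 25.0 for r = 4 and 20.0 for r = 5 (r assumed).

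**5. How likely is at least one increase?** The documents give no rate. If each patient independently has probability q of an increase by month 3, the chance of at least one among 10 is 1 − (1 − q)^10:

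| q (assumed) | Chance of at least one |
|---|---|
| 5% | 40% |
| 10% | 65% |
| 20% | 89% |
| 30% | 97% |

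This is the chance of any increase, not of one that turns a non-responder into a responder.

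**6. Why the durability denominator must be fixed.** Suppose 4 patients respond at month 3 by observed CDASI and 3 maintain: 3/4 = 75%. If the fourth had a background increase before month 3 and was dropped from the denominator for it, durability would become 3/3 = 100%. With the denominator fixed it stays at 3/4.

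**The case against.** The strongest reply is that other parts of the protocol already limit the problem.

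- The synopsis says "Treatment will be discontinued at disease progression or unacceptable adverse events", and Section IX allows withdrawal for little or no therapeutic effect or by the investigator's decision, with the reason documented. A patient doing badly enough to need escalation may leave by these routes.
- A flare may be recorded as an adverse event under Section VIII, and the causality definitions there ask the investigator to weigh other medications.

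These points narrow the pathway without closing it. Withdrawal is discretionary. Progression is written as a CDASI rise together with MMT-8 worsening and a DLQI rise, so on a literal reading a skin-only flare does not meet it. The adverse-event text concerns the causes of events, not response. An increase made without any worsening leaves no stated trace.

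Three further objections stand and limit the claim.

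- A reader might infer that background changes will go unrecorded. The documents do not show that. The CRF was not seen and may hold a medication page. The missing analysis rule in Section VI is established, while the missing record is an inference from the Schedule of Events.
- A reader might infer that the ORR will be inflated. The documents give no frequency of increases, and the only change they foresee, towards monotherapy, is a reduction.
- Counting every background increase as non-response is partly a choice of estimand. Reporting response regardless of background is also legitimate in a small descriptive study, so the stricter count belongs beside the as-observed result and should not replace it.

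**Conclusion.** The point holds for the text available, which excludes the opening pages and the CRF. Stability is an entry condition only, response and durability rest on CDASI alone, and no handling of a later background change is stated. A CDASI fall of at least 4 points after an increase therefore counts as an apremilast response.

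The size is 10 percentage points of ORR per converted patient, and 20 to 33 points of durability if there are 5 to 3 month-3 responders. Both are zero if no increases occur. The analysis is descriptive, with no threshold or decision rule, so the effect is a shift in an estimate and not a reversed conclusion.

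It would also be too strong to infer that stable background therapy would by itself establish attribution to apremilast. Without a control arm it would not. Recording and reporting changes only shows how far the result depends on them. The change is worth making because it is cheap and because dates not collected during the study may be hard to recover afterwards.

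**What to change.** 1. Add to the Schedule of Events, and to the CRF if not already there, a record of systemic and topical dermatomyositis therapy at baseline and every later visit, with dose and start, stop and change dates.
2. State in Sections IV and VI that the month-1, month-3 and month-6 response rates are reported two ways, side by side. The first is as observed. The second counts as a non-responder any patient who, after day 0 and before the assessment, started a new dermatomyositis therapy or went above the day-0 dose of an existing one. A return to the day-0 dose after a reduction is not an increase. In the second analysis this rule takes precedence over LOCF.
3. For durability, use all month-3 responders by observed CDASI as the denominator in both analyses. In the second, a patient who started a new therapy or went above the day-0 dose before month 6 counts as not maintained.
4. List every background increase and reduction per patient beside the response, durability and monotherapy results.

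**Cost.** One record row, a second set of proportions and one listing. A true responder whose background was raised for another reason counts as a non-responder in the second analysis. Each such patient lowers that rate by 10 points, for example from 3/10 to 2/10 (exact 95% CI 2.5% to 55.6%). The as-observed result and the listing make this visible. The proposal concerns recording and analysis only. Which background changes are clinically allowed is for the sponsor and the investigator to state.

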Skin biopsies from lesional skin will be performed before treatment with apremilast and after 3 months of treatment for gene expression profiling and IHC stain. IHC will be performed on the protein product of the genes showing the largest fold change from the RNA-sequencing.

All investigators (PI and Sub-Is) will be trained on how to screen the patients per the MMT-8 score tool.

V. STUDY ENROLLMENT AND TIMELINES

1. # of Patients Expected to Enroll: 10

2. Date of planned FSI: 04/02/2018

3. Date of planned LSI: 11/01/2018

4. Date of planned LSO: 05/01/2019

5. Patient treatment duration (# months): 6 months

6. Is an interim Analysis Planned? Yes

7. Date on planned Interim Analysis: 03/01/2019

8. Date of planned final report: 06/03/2019

9. Are patients reported outcomes measured: Yes

VI. STATISTICAL PLAN:

Results of the study will be analyzed using descriptive statistics:

- Proportion of patients with complete ORR at 1,3 months
- Proportion of patients with partial ORR at 1,3 months
- Proportion of patients with complete durability response at 6 months for the 3 months responders
- Proportion of patients with partial durability response at 6 months for the 3 months responders
- Proportion of patients with complete response at 6 months
- Proportion of patients with partial response at 6 months
- Mean change from baseline in muscle enzymes (CK and aldolase in patients with muscle disease)
- MMT-8 change will be calculated as mean change from baseline at 1,3 and 6 months
- DLQI change will be calculated by identifying the proportion of patients with minimal clinically important difference of at least 5 points.

Missing data will be handled using the last observation carried forward approach (LOCF).

GEP will be analyzed using inferential statistics with a False Discovery Rate (FDR) of < 0.05 .

VII. INFORMED CONSENT:

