If the sequela of an overdose is an SAE, then the sequela must be reported on an SAE report form. The overdose resulting in the SAE should be identified as the cause of the event on the SAE report form but should not be reported as an SAE itself.

In the event of an overdose, the patient should be monitored as appropriate and should receive supportive measures as necessary. There is no known specific antidote for apremilast overdose. Actual treatment should depend on the severity of the clinical situation and the judgment and experience of the treating physician.

Overdose for this protocol, on a per dose basis, is defined as ingestion of any more than the amount prescribed of apremilast (or matching placebo) tablets in any 24 hour period whether by accident or intentionally.

IX. PATIENT'S WITHDRAWAL

The patient may withdraw from the study or withdrawn due to the many reasons:

- Loss to follow-up

- Adverse Event
- Non-Compliance
- Minimal/no therapeutic effect.
- Withdrawal of the patient by the investigator.
- Other reasons

Efforts should be made to follow-up patients with adverse events to know the final outcome of the event.

The patient and/or investigator, both have the right to terminate the patient's participation in the study. The reason for termination/withdrawal will be documented.

X. DATA MANAGEMENT

All data must be entered into the clinical data management system before initiating treatment. Electronic case report form (CRF) will be used for the collection of all study data entry at the clinical trial site. The PI will enter the data. All requested information must be entered in the CRF in a timely manner and the CRF for each visit must be completed during the visit. The completed CRF must be reviewed, signed and dated by the PI as well as any missing data should be recorded. Files containing electronic data will be password protected and encrypted and will be closed when computers are left unattended. Contact lists, recruitment records, or other documents that contain Protected Personally Identifiable Information (PPII) will be stored securely in locked cabinets or rooms and access to key codes will be limited.

XI. PUBLICATION PLAN

1.Target Journal: JAAD

2. If Other Specify: JAMA

3. Date of Planned manuscript: September 2019

XII. SUPPORT REQUESTED FROM CELEGENE RESOURCES

1. Requesting Study Drug? Yes

2. Requesting Study funding? Yes

3. Support Requested from other companies? No

4. Non-Celegene Support Sources: None

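### Ten before/after pairs is the maximum that 10 patients can give, no calculation supports the claim of sufficient power, and the lesional-skin rule at month 3 conflicts with complete response

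*Combined protocol and SAP*

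**What the plan says.** **Size and power.** Section 10.B.a (Gene expression profiling) says of the sample number: "10 samples before treatment and 10 samples after treatment) is expected to yield sufficient statistical power". The support offered is that "smaller numbers have been used in similar approaches to investigate drugs' mechanism of action (usually three samples"). No effect size, variance, gene count or target power is given. Section V gives the number "of Patients Expected to Enroll: 10". The Schedule of Events has one skin biopsy at baseline and one at month 3, and none at early termination.

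**Analysis.** Section 10.B.a says "differential expression will be analyzed using EB-seq" and describes the comparison as one between two groups, without mentioning pairing. Section VI adds "GEP will be analyzed using inferential statistics with a False Discovery Rate (FDR) of" less than 0.05. Missing data are to be handled by LOCF.

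**Losses.** Section 7 (Brief Study Synopsis) ends treatment at progression or unacceptable toxicity. Section IX lists reasons for withdrawal that include loss to follow-up, adverse events, non-compliance and "Minimal/no therapeutic effect". No replacement rule, over-enrolment or attrition allowance appears.

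**Tissue.** The synopsis says "5 mm skin biopsies from lesional skin will be performed before treatment with apremilast and after 3 months of treatment", and section IV.3 agrees: "Skin biopsies from lesional skin will be performed before treatment with apremilast and after 3 months of treatment". Section 10.A.a names lesions for the baseline punch only and leaves the month-3 site open. Section IV.1 defines complete response as a CDASI of zero and partial response as a fall of at least 4 points.

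**The concern.** Two separate problems bear on the same 20 samples.

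The first is the count. Ten month-3 samples from 10 patients requires every patient to reach month 3 and give usable tissue. The protocol lists several ways in which that can fail, and LOCF cannot supply a missing biopsy. A maximum is therefore presented as the planned number, and a power claim without a calculation is attached to it.

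The second is what the month-3 sample represents. If it must be lesional, a patient at CDASI zero has nothing eligible to biopsy, and in a partial responder the rule selects whatever has not cleared. The contrast then under-represents the skin in which the drug worked, although the stated purpose of the sequencing is to learn how it works. In an unpaired two-group comparison, the baseline group would also contain patients who are absent from the month-3 group.

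**Working it through.** **1. The protocol's own figure.** 10 patients × 1 biopsy per visit = 10 before + 10 after. The count reproduces, with a margin of 10 − 10 = 0. The power statement cannot be reproduced, because none of its inputs is given.

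**2. Chance of obtaining all 10 pairs.** The documents give no loss rate. Let q be the assumed chance, independent between patients, that a patient gives no usable month-3 sample for any reason. Then P(10 pairs) = (1 − q)^10 and the expected number of pairs is 10(1 − q).

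| q | P(all 10 pairs) | Expected pairs |
|---|---|---|
| 2% | 82% | 9.8 |
| 5% | 60% | 9.5 |
| 10% | 35% | 9.0 |
| 20% | 11% | 8.0 |
| 30% | 3% | 7.0 |

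The probability falls below one half when q exceeds 1 − 0.5^(1/10) = 6.7%.

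**3. What a given number of pairs could detect.** The FDR limit of 0.05 is the protocol's. All else here is assumed: 15,000 genes, 5% truly changed (750 changed, 14,250 not), 80% power, and a two-sided paired t-test per gene as a stand-in for EB-seq.

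Per-gene alpha = FDR × changed × power / [unchanged × (1 − FDR)] = 0.05 × 750 × 0.8 / (14,250 × 0.95) = 30 / 13,537.5 = 0.0022.

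Power comes from the noncentral t distribution with n − 1 degrees of freedom and noncentrality d√n, where d is the mean within-patient change divided by the SD of those changes.

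| Pairs | Detectable d at 80% power | Power at d = 1.67 | Power at d = 2.0 |
|---|---|---|---|
| 10 | 1.67 | 80% | 94% |
| 9 | 1.84 | 69% | 88% |
| 8 | 2.07 | 56% | 76% |
| 7 | 2.40 | 40% | 60% |

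With three pairs, power at d = 1.67 is about 2%. Under these assumptions, having more than three samples does not show that 10 are enough.

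**4. Sensitivity to the share of changed genes.** At 10 pairs the detectable d is 2.09 if 1% change, 1.67 if 5%, 1.50 if 10% and 1.21 if 30%. The range from 1.21 to 2.09 is wider than the rise from 1.67 to 2.40 caused by losing three pairs.

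**5. Tissue rules side by side.**
- Synopsis and section IV.3: lesional skin at both times.
- Section 10.A.a: lesional at baseline, month-3 site unspecified.
- Section IV.1: complete response is CDASI zero.

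Under the synopsis and section IV.3, a complete responder has no eligible site and a partial responder contributes only residual lesions. Under section 10.A.a, either patient could be sampled at the baseline site. The protocol does not say which section governs.

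**The case against.** The strongest reply is that the documents do not show that the target will be missed. A reader might infer that 10 pairs will probably not be reached. That holds only if combined loss exceeds about 6.7% per patient, and no dropout or complete-response rate is given; at 5% loss, all 10 pairs are obtained 60% of the time. This part of the objection stands, and the point is limited to 10 being a ceiling.

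A reader might also infer that the missing samples would come mainly from treatment failures and complete responders. Section IX lists other reasons without frequencies, and the synopsis definition of progression joins three conditions with *and*, which read literally makes such stops rarer. Selective loss is possible, but its dominance is not shown. Nor is it established that complete responders cannot supply a sample: section 10.A.a does not require lesional tissue at month 3, and no text rules out the earlier site. What stands is an unresolved conflict of wording, with a predictable bias if the lesional version is followed.

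On power, the 1.67 SD series starts at 80% by construction, so any loss must fall below 80%. At 2.0 SD, power is still 88% with nine pairs. The paired t-test is not the planned method, and the gene assumptions are illustrative. All of this is true, but it also shows that sufficiency depends on inputs the protocol never states.

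Finally, gene expression is exploratory, the response-rate analysis is untouched, and seven to nine pairs still exceed the cited precedent. This limits the weight of the point. It does not support the power claim that the protocol chose to make.

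**Conclusion.** The point holds in three parts.

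1. Ten pairs is the maximum available. The chance of reaching it is 60% to 3% over assumed losses of 5% to 30%. These are scenarios, not forecasts.
2. No calculation supports the claim of sufficient power at any number of pairs. Under one stated set of assumptions the detectable change is 1.67 SD at 10 pairs, 2.07 at 8 and 2.40 at 7. At 10 pairs it ranges from 2.09 to 1.21 SD as the share of changed genes goes from 1% to 30%.
3. The tissue passages conflict. If the lesional wording governs, the before/after contrast is biased towards non-response. The size of that bias cannot be calculated from the documents.

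The second and third parts do not depend on any assumed loss rate. The amendment is worth making, at a weight suited to an exploratory objective.

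**What to change.** 1. **Biopsy site.** Reconcile the synopsis, section 10.A.a and section IV.3. The month-3 biopsy already planned should come from the same lesion area as baseline, away from the first punch scar, whether or not it is still lesional. Record lesional status and show results overall and by status. The cost is that the month-3 samples mix cleared and active skin, which the display by status makes visible.
2. **Size and power.** In section 10.B.a, state the size as up to 10 pairs. Replace the claim of sufficient power with the detectable effect over a range such as 7 to 10 pairs, with assumptions listed and the share of changed genes varied. Alternatively, drop the claim and label the analysis exploratory. Either way the stated position becomes less favourable.
3. **Analysis.** In sections 10.B.a and VI, specify that before and after samples are compared within patient, and say how the chosen method uses the pairing. Report the number of missing pairs with reasons. A complete-pairs analysis does not remove selective loss, so the reasons are needed to judge it.

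All three are changes of protocol text, with no added patient or biopsy. Only the first changes what is sampled, so it needs to be settled before month-3 biopsies are taken.
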